4 month assumptions: 5% incidence AF in monitored, 0.5% in non-monitored.

[figure not shown]
	Sample Size Active Monitoring	Sample Size Delayed Monitoring	Event Rate Active Monitoring	Event Rate Delayed Monitoring	Power
As Designed	1000	1000	5%	0.5%	>0.99
Minimal Size	320	320	5%	0.5%	0.90
Minimal Size, Increased Event Rate	430	430	5%	1.0%	0.90

12 months assumptions: 7% incidence AF in monitored, 2% in the observational control arm.

	Sample Size Active Monitoring	Sample Size Matched Observational Cohort	Event Rate Active Monitoring	Event Rate Delayed Monitoring	Power
As Designed	2000	4000	7%	2%	>0.99
Minimal Size	400	400	7%	2%	0.90
Minimal Size, Increased Event Rate	1278	1278	7%	4%	0.90

3-year assumptions:

- 10% prevalence of AF in both monitored and observational control arms.
- A 7.5% event rate in observation cohort (based on ACTIVE A data) and a 50% reduction in the monitored cohort due to earlier diagnosis prior to having an event or symptom.

Power = 0.81 for log rank test with assumptions as below (rates are cumulative):

	Actively Monitored		Control	
Sample size with AF (10% prevalence in both groups)	n=200		n=400	
	Diagnosis Rate	Event Rate	Diagnosis Rate	Event Rate
6 months	5%	1%	0.5%	4%
15 months	7%	2%	3%	9%
36 months	10%	5%	10%	12%

A separate, detailed statistical analysis plan will be developed.

8. Possible Benefits

It is possible that participants could benefit by receiving a diagnosis of AF before they would otherwise, which could possibly lead to changes in therapy that might decrease their risk of thromboembolic events.

As determining the optimal method for population screening for AF is recognized as being an important unmet need, the results of this study could benefit a substantial proportion of the population through helping identify and refine screening methods. In addition, participation in this study will provide a greater understanding of the characteristics (e.g. frequency, duration, rate, time of day) of arrhythmias episodes that are or are not associated with symptoms.

9. Possible Risks and Analysis of Risk/Benefit Ratio

There is minimal risk to a patient receiving cardiac rhythm monitoring and, in general, complications are related to the adhesive that affixes the ZIO XT Patch to the subject. The FDA has cleared the ZIO XT Patch for use for patients who do not have known skin allergies or a family history of skin allergies. Company experience for skin allergies in 2011 is 0.02% in over 30,000 patients.

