7. STATISTICAL METHODOLOGY

Sample Size Determinations

For the 4-month RCT, the sample size of 1,000 subjects for each group (immediate monitoring = active monitoring and delayed monitoring=no active monitoring) achieves >99% power to find a difference between an expected incident atrial fibrillation rate of 5% in the active monitoring group and an expected incident atrial fibrillation rate of 0.5% group without active monitoring with a two-sided alpha of 0.05. This sample size also achieves adequate power for the detection of the difference between the two groups at lower event rates, achieving 98% power for an expected rate of 2% in the active monitoring group and 0.1% in the delayed monitoring group with a two-sided alpha of 0.05.

For the Matched Observational Cohort Study, at 12 months, sample sizes of 2,000 subjects in the active monitoring group (immediate monitoring + delayed monitoring) and 4,000 subjects in the matched control group achieves >99% power to find a difference in the expected atrial fibrillation rate of 7% in the active monitoring group and 2% in the matched control group with a two-sided alpha of 0.05.

For the Matched Observational Cohort Study, based on an expected prevalence of atrial fibrillation of 10% in both the actively monitored (i.e., n=200) and matched control cohorts (i.e, n=400), a 7.5% event rate/year in the matched observational cohort and a 50% reduction in events in the actively monitored cohort due to earlier diagnosis prior to having an event or symptom, the expected combined event rate is 5% in the actively monitored subjects and 12% in the matched observational controls. Given these assumptions, the sample size yields 81% power to detect the expected difference in time to event with a log rank test with a two-sided alpha of 0.05.

Descriptive Statistics

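### The 3-year power statement lists a 7.5% control rate, a 50% reduction, 5% vs 12% and 81% power, and these do not agree; the 81% belongs to 5% vs 12%, a 58% reduction

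*SAP*

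**What the plan says.** SAP Section 7, under Sample Size Determinations, takes 10% AF prevalence in each cohort (200 monitored, 400 matched controls). It assumes "a 7.5% event rate/year in the matched observational cohort and a 50% reduction in events in the actively monitored cohort". In the same sentence it concludes that "the expected combined event rate is 5% in the actively monitored subjects and 12% in the matched observational controls", and it continues: "Given these assumptions, the sample size yields 81% power to detect the expected difference in time to event with a log rank test", at a two-sided alpha of 0.05.

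Protocol Section 7, under its 3-year assumptions, also has "10% prevalence of AF in both monitored and observational control arms" and then "A 7.5% event rate in observation cohort (based on ACTIVE A data) and a 50% reduction in the monitored cohort". No time unit is attached to that 7.5%. A table of cumulative rates follows, and the protocol ties its power of 0.81 to that table:

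| Month | Monitored: diagnosed | Monitored: events | Control: diagnosed | Control: events |
|---|---|---|---|---|
| 6 | 5% | 1% | 0.5% | 4% |
| 15 | 7% | 2% | 3% | 9% |
| 36 | 10% | 5% | 10% | 12% |

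Neither document shows how 7.5% and a 50% reduction become 12% and 5%.

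**The concern.** The SAP offers 5%, 12% and 81% as consequences of 7.5% per year and a 50% reduction. Half of 12% is 6%, not 5%, and three years at 7.5% per year comes to well over 12%. The stated inputs therefore do not produce the stated rates, and the power is calculated from the rates.

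This is the only power calculation for a 3-year outcome in either document. It supports the question of whether earlier detection reduces thromboembolic events. A reader who pairs 50% with 81% does not know what effect the comparison was sized to detect, and could misjudge a null or an imprecise result in the AF sub-population.

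**Working it through.** **Inputs.** n = 200 and 400, two-sided alpha 0.05, 36-month rates 5% and 12%, 7.5% per year, 50% reduction (SAP Section 7); the cumulative table (Protocol Section 7).

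**1. Reproduce the 81%.** Pooled two-proportion formula, with p1 monitored, p2 control and p̄ the pooled rate:

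power = Φ{[(p2 − p1) − 1.96·SE0] / SE1}, where SE0 = √[p̄(1 − p̄)(1/200 + 1/400)] and SE1 = √[p1(1 − p1)/200 + p2(1 − p2)/400].

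At 5% vs 12%: p̄ = (10 + 48)/600 = 0.0967, SE0 = 0.0256, SE1 = 0.0224. The argument is (0.070 − 0.0502)/0.0224 = 0.886, so power = 0.812. This is the plan's 81%. A simulated log-rank test gives 0.82 with exponential times and 0.83 along the protocol's 6/15/36-month path.

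**2. The reduction in the table.**
- Month 6: 1 − 1/4 = 75%.
- Month 15: 1 − 2/9 = 78%.
- Month 36: 1 − 5/12 = 58%.

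No row shows 50%.

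**3. From 7.5% per year to 3 years.** Constant hazard: 1 − exp(−0.225) = 20.1%. Annual compounding: 1 − 0.925³ = 20.9%. Simple addition: 22.5%. None is near 12%. The protocol's control path follows 7.5% per year at first: 1 − exp(−0.0375) = 3.7% at month 6 (table 4%) and 1 − exp(−0.09375) = 8.9% at month 15 (table 9%). From month 15 to 36 it slows to 1 − (0.88/0.91)^(12/21) = 1.9% per year.

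**4. Keep 12% and apply 50%.** At 6% vs 12%: p̄ = 0.100, SE0 = 0.0260, SE1 = 0.0234. The argument is (0.060 − 0.0509)/0.0234 = 0.389, so power = 0.651. Simulated log-rank: 0.66–0.67. If 50% means a hazard ratio of 0.5, the monitored rate is 1 − 0.88^0.5 = 6.2% and pooled power is 0.617.

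**5. Keep 7.5% per year and 50%.** Same pooled formula:

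| Reading | Monitored vs control | Power |
|---|---|---|
| Constant hazard, hazard halved | 10.6% vs 20.1% | 0.855 (simulated log-rank 0.864) |
| Constant hazard, 3-year risk halved | 10.1% vs 20.1% | 0.90 |
| Compounded, 3-year risk halved | 10.4% vs 20.9% | 0.91 |
| Simple addition, halved | 11.25% vs 22.5% | 0.935 |

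**6. Sensitivity to the formula.** At 5% vs 12% and then 6% vs 12%, Freedman gives 0.766 and 0.624, and Schoenfeld 0.906 and 0.755. The fall between the two is similar to that in the pooled figures. Freedman on the first row of step 5 (hazard ratio 0.5; 200 × 0.1064 + 400 × 0.2015 = 101.9 events) is Φ[√101.9 × √0.5 × 0.5/1.25 − 1.96] = Φ(0.895) = 0.81. That formula can therefore return 81% from the two stated inputs, but only with 3-year rates of 10.6% and 20.1%, not the 5% and 12% to which both documents attach the figure.

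**The case against.** The strongest defence is that the power figure itself is not wrong. The protocol attaches 0.81 to a table that discloses the rates, the SAP gives 5% and 12% just before its 81%, and the calculation reproduces from them. On this view 50% is a loose label. The reproduction stands, and it is why one of the repairs below leaves 81% untouched. It does not remove the contradiction, because the SAP carries no table and states the 50% as an assumption on which the 81% rests.

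A second defence is that delayed diagnosis explains the control path. The diagnosis columns make this plausible: controls go from 3% to 10% diagnosed between months 15 and 36, just when their event rate slows. Neither document says so, and a reader cannot rebuild 12% or 5% from the text.

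A reader might also infer something stronger: that the comparison is underpowered, that true power is 65%, or that 81% always needs an effect larger than 50%. The documents do not support this. Those statements hold only with controls fixed at 12%, which is itself underived. If both stated inputs are kept, the pooled formula gives power above 81%. The 7.5% is also the only one of these figures for which a source is named.

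Finally, the consequence is limited: this is a secondary, non-randomised sub-population comparison. That is accepted.

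**Conclusion.** The concern holds as an inconsistency, not as a finding of low power. With 200 vs 400 and two-sided 0.05, the 81% corresponds to 36-month rates of 5% vs 12%, a 58% reduction. It does not follow from the 50% reduction stated beside it, and 12% does not follow from a constant 7.5% per year. On the pooled formula that reproduces the plan's figure, power is about 65% if 12% and 50% govern, 81% if 12% and 5% govern, and about 86–93% if 7.5% per year and 50% govern. Which was intended cannot be told from the documents.

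These figures assume that the projected 200 and 400 AF cases are reached and that nobody is censored before 36 months. The simulations also take exponential or piecewise-exponential event times. The power method is not named. That is a missing detail rather than an error, though the formula does move the figure.

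**What to change.** State one consistent set of figures in both documents. Any of these would do:

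- (a) 81% power for 36-month cumulative rates of 12% vs 5%, described as a 58% reduction, with the 50% removed or labelled as not the powered effect.
- (b) 12% vs 6%, a 50% reduction, with power restated as about 65%.
- (c) 7.5% per year and a 50% reduction, with 3-year rates restated as about 20% vs 10–10.6% and power as about 86–90%.

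Under (a) or (b), state the assumption that takes 7.5% per year to 12% at 36 months (for example a lower rate once controls are diagnosed, if that was meant), or drop the 7.5%. Wherever the protocol keeps its 7.5%, add the time unit.

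The cost is a few sentences in each document. Under (a) the stated power stays; under (b) it falls; under (c) it rises. Enrolment, the primary analysis and the analysis methods are unchanged.

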- Aetna Compassionate Care Program (ACCP) participants – individuals with advanced illness and limited life expectancy

Through the use of the above inclusion and exclusion criteria, but not excluding patients with a diagnosis of atrial fibrillation or flutter, we expect to identify a population with an overall prevalence of known AF of 10-15%. Based on prior studies supporting that 30% of the total AF population is undiagnosed, then the total AF population (X) = diagnosed AF population (0.7X) + undiagnosed AF population (0.3X). Therefore with a 12% prevalence of diagnosed AF representing only 70% of the total AF population that would suggest that the true total AF population prevalence is 17%, and therefore the prevalence of undiagnosed AF would be ~5%.

[figure not shown]
Participant Recruitment

Eligible Aetna members will be contacted by letter, electronically or paper, (Appendix 1) with information about the study and an invitation to learn more via a study-specific web site as well as the option to discuss with a research coordinator. Once an individual agrees to participate they will be directed to an online Informed Consent Document, or if they prefer, one will be mailed to them.

A conservative estimate is that 5% of the approached population will agree to participate in the study. With an estimated >100,000 eligible participants to approach this should allow for the recruitment of a total of 2000 individuals for randomization and allow for development of a matched observational cohort of 4000 individuals.

It is anticipated that 10,000 invitations will be sent out to eligible Aetna members on a rolling basis every one to two weeks with invitations continuing until ~2250 (to account for an assumed 12% drop-out in first year) individuals have agreed to participate and signed the informed consent.

Study Flow

Randomized Cohort

Following informed consent individuals will be randomized to either the immediate screening arm or the delayed screening arm. All individuals randomized to immediate screening will be sent their monitoring device(s) immediately after signing their informed consent. Their 4 months of monitoring will begin the first day their monitoring device is activated. Those randomized to delayed monitoring will receive their monitoring device(s) 4 months after the date of their informed consent being signed, with their 4 months of monitoring also starting the first day their monitoring device is activated.

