During the 4-month monitoring period all individuals will undergo continuous single-lead ECG monitoring with a wearable patch (iRhythm ZIO® XT Patch) during the first and last 2 weeks of the 4-month study period (total of 4 weeks).

Consenting participants will also be invited to participate in a ~500 person sub-study to wear an additional monitoring device; a wristband photoplethysmography-based device (Amiigo). Enrollment in this sub-study will be limited to individuals who already own and use a smartphone (iOS or Android). Volunteers will be asked to sign a second informed consent to participate in this sub-study.

Monitoring Devices

All individuals randomized to active screening will receive a ZIO XT Patch (<http://www.irhythmtech.com/zio-solution/zio-patch/>). The ZIO XT Patch will be mailed to the participant's home with instructions how to place and activate the patch. A link to an instructional video will also be provided as well a call-in number for support.

They will be asked to wear it for the first 2 weeks, and again during the final 2 weeks of the 4-month monitoring period. While wearing the patches a single-lead ECG is recorded

continuously. After the 2-week monitoring period the patch is mailed back to iRhythm in a pre-prepared package where the rhythm is analyzed.

A second exploratory method of rhythm detection in a self-identified subset of the same patients will be carried out using a wristband developed by Amiigo (<https://amiigo.com/>) that will allow for long term, non-obtrusive monitoring on a daily basis throughout the 4 month period. The Amiigo determines resting pulse rate using photoplethysmography; a technique

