Subjects randomized to the delayed monitoring cohort for the RCT will be actively monitored following completion of the 4 month RCT follow-up period (for which they serve as unmonitored controls). Subjects in the delayed monitoring group will receive their first Zio patch 4 months following their date of enrollment. The first Zio patch will be worn during the first two weeks of the 4-month monitoring period. A second Zio patch will be sent to subjects in the delayed monitoring group for wear during the final two weeks of the 4-month monitoring period.

Matched Observational Cohort Study: Actively Monitored (Immediate and Delayed) vs. Matched Observational Controls

For the Matched Observational Cohort study, the actively monitored group will include all subjects in the RCT who were randomly assigned to either active monitoring period (immediate or delayed).

Two matched controls will be selected for each of the 2,100 actively monitored subjects in the RCT (1,050 immediate + 1,050 delayed) from 1) the pool of subjects from the original eligible cohort who continue to be eligible based on monthly database updates and did not receive an invitation to enroll. Matching will be performed using the following criteria:

- Sex (exact)
- Age (exact by year of birth)
- CHA₂DS₂ VASc score (exact score)

CHA₂DS₂ VASc scores are re-calculated for monitored subjects at time of enrollment (updating scores calculated for eligibility of original pool). CHA₂DS₂ VASc scores are re-calculated for the pools of potential matched controls following the monthly update of the Aetna claims database and immediately prior to application of the matching protocol. Actively monitored subjects and controls will be matched on these updated CHA₂DS₂ VASc scores. Exact matches are prioritized. Matching of CHA₂DS₂ VASc score \pm 1 will be the next option if 2 exact match controls are not found for a monitored subject.

Start date for determination of outcomes from Aetna databases for both monitored subjects and matched controls will be the date of enrollment of the monitored subject. End date for the analysis of prevalence of atrial fibrillation, initiation of anticoagulation and initiation of other AF-specific interventions will be 12 months from the actively monitored subject's date of enrollment (by exact month and day). End date for analysis of outcomes at 3 years will be 3 years from the actively monitored subject's date of enrollment (by exact month and day).

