Descriptive statistics (frequency of categorical variables; means (or medians), standard deviations (or interquartile range), and ranges of continuous variables) will be calculated for all variables (endpoints and covariates for both the Randomized Controlled Trial and the Observational Follow-up Study). Distributions of all variables will be examined for outliers and normality (continuous variables) both graphically and by descriptive statistics. Descriptive statistics will also be calculated for the following sub-populations: 1) subjects included in the per-protocol analyses specified below; 2) subjects who receive a diagnosis of atrial fibrillation/atrial flutter by the end of 3 years; and 3) subjects enrolled in Medicare (for analysis

the combined endpoint that includes death). Bivariate analyses will be used to examine differences in subject characteristics at enrollment 1) by randomized group, to assess the effectiveness of randomization, and 2) by actively monitored vs. matched observational control cohort to assess effectiveness of matching. Bivariate associations will be assessed using statistical methods appropriate for the variable types (Fisher's exact for categorical variables; t-test, ANOVA or non-parametric equivalents for continuous variables).

Descriptive statistics for device usage will be calculated separately for immediate monitoring group and the delayed monitoring group for their respective active monitoring periods, starting at date of enrollment and ending with completion of monitoring with final patch.

Analysis of Randomized Controlled Trial

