We will use the same time to event analyses with 3 year follow-up to evaluate the same disease and hospitalization endpoints among the subset of subjects included in the matched observational cohort study who receive a diagnosis of atrial fibrillation during the study. All analyses will be performed as intention-to-treat with parallel exploratory analyses performed on per-protocol basis restricted to subjects enrolled in the monitoring group who underwent Zio patch monitoring.

Analysis of Safety Endpoints

For analysis of safety endpoints at 3 year follow-up, we will compare incidence of hospitalization for bleeding per person-years of follow-up between the actively monitored group and the matched observational control group. Hospitalizations for bleeding will also be characterized by length of stay. Other safety outcomes will be characterized for the period of active monitoring in the active monitoring group only. These include Incidence of non-AF, but other actionable heart rhythms captured by the Zio patch device, specifically: 1) Atrial Tachycardia with variable block of > 30 seconds; 2) Ventricular Tachycardia >5 beats; 3) Pauses \geq 5 seconds; and 4) AV block. We will also characterize early discontinuation of active monitoring in monitored cohort by cause and time to event.

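### The SAP starts the delayed group's active monitoring period at enrolment, about 4 months before its first patch is due; this contradicts the rest of the plan and would distort any time-based usage or discontinuation result that uses that start

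*SAP*

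**What the plan says.** SAP section 7, Descriptive Statistics, sets the rule. Usage is to be summarised by randomised arm, and the window for those summaries reads: "for their respective active monitoring periods, starting at date of enrollment and ending with completion of monitoring with final patch". One start, enrolment, is given for both groups.

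SAP section 4, Delayed Monitoring Group, says that these subjects "will be actively monitored following completion of the 4 month RCT follow-up period", during which they act as unmonitored controls. It adds: "Subjects in the delayed monitoring group will receive their first Zio patch 4 months following their date of enrollment".

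Protocol section 4, Study Flow, starts monitoring at activation in both groups. For the immediate group: "Their 4 months of monitoring will begin the first day their monitoring device is activated". For the delayed group, the device comes 4 months after consent, "with their 4 months of monitoring also starting the first day their monitoring device is activated".

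SAP section 3 lists the incidence, timing and cause of stopping active monitoring as safety analysis 3. SAP section 7, Analysis of Safety Endpoints, confines the device safety outcomes to the time under active monitoring and says: "We will also characterize early discontinuation of active monitoring in monitored cohort by cause and time to event". It names no time origin.

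**The concern.** A subject cannot be in an active monitoring period while serving as an unmonitored control. The word *respective* suggests that a separate period was meant for each group, but the clause that follows gives both the same start. A programmer who follows it literally would open the delayed group's window about 4 months early.

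Device exposure is the intervention in this study, so how it is timed matters. Under the written rule, a delayed-group subject who behaves exactly like an immediate-group subject could appear slower to start and less adherent, only because of the assigned wait. The timing of discontinuation is also exposed. It is a listed safety endpoint analysed by time to event, and the Descriptive Statistics sentence is the only place where the SAP gives an explicit start date for the active monitoring period.

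**Working it through.** The plan states no figure for this point, so there is none to reproduce. The check is date arithmetic.

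**Inputs**
- Wait from enrolment to first patch, delayed group: 4 months (SAP section 4).
- Length of monitoring: 4 months from activation (Protocol section 4).
- Planned wear: "during the first and last 2 weeks of the 4-month study period (total of 4 weeks"), that is 2 × 14 = 28 days.
- Monitored subjects: 1,050 immediate + 1,050 delayed = 2,100 (SAP section 4).
- Month length: 365.25/12 = 30.44 days, so 4 months = 121.75 days.
- Lag from enrolment (immediate) or from the month-4 date (delayed) to activation: not given. I assume 0 to 30 days and show the range.

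**Window length**
- Immediate group from enrolment, no lag: 121.75 days.
- Delayed group as written, no lag: 121.75 + 121.75 = 243.5 days.
- Part of the delayed window before any patch is due: 121.75/243.5 = 50%. With a 30-day lag: 121.75/273.5 = 44.5%.

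**Planned wear as a share of the window, same 28 days of wear**

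| Assumed lag | Immediate | Delayed, as written |
|---|---|---|
| 0 days | 28/121.75 = 23.0% | 28/243.5 = 11.5% |
| 14 days | 28/135.75 = 20.6% | 28/257.5 = 10.9% |
| 30 days | 28/151.75 = 18.5% | 28/273.5 = 10.2% |

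With activation as the start, both groups have a nominal window of 121.75 days and a planned share of 23.0%, whatever the lag.

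**Time to discontinuation, if enrolment were the origin**
- Each delayed-group time rises by 121.75 days, plus any activation lag. A stop 14 days after activation would read as day 14 + 121.75 = 135.75, about day 136.
- An immediate-group time rises only by the activation lag.

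**Share of the cohort affected:** 1,050/2,100 = 50%.

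**What does not move.** SAP section 5 lists total wear time and analyzable recording time as the usage variables (covariates 12 and 13), and SAP section 2 shows that they come from the device. Neither can accrue before a patch is worn, so both are the same under either start. The primary AF comparison has its own follow-up window in SAP section 4 and does not use this one.

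**The case against.** The strongest reply is that this is a drafting slip with little effect. Four parts of that reply stand.

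- The usage variables that the SAP names do not depend on the window. Share of the period worn and time to first wear are not named anywhere in the plan. The 23.0% against 11.5% comparison shows what the window would do to such a measure; it does not describe a planned result.
- The usage summaries are descriptive and separate by group, with no between-group test specified.
- The Descriptive Statistics sentence covers device usage only. Discontinuation is handled in another paragraph, limited to the time under active monitoring. Read with SAP section 4 and the protocol, that wording points towards activation.
- Activation dates are recorded, so the intended window can be recovered.

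A reader might infer more than the documents support:

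- *That discontinuation results for half the cohort will be wrong.* The origin is unstated, not shown to be enrolment, so the 4-month shift is conditional.
- *That a pooled discontinuation curve would be flat for its first 4 months.* No pooled curve is specified. If there were one, immediate-group subjects could discontinue from the start. The per-protocol definition in SAP section 4 also foresees delayed-group withdrawals before month 4, which would add early events if counted. The early part could be diluted, not flat.
- *That the tolerability objective is compromised.* That objective compares the patch with the wristband, and the SAP labels it exploratory. It does not compare immediate with delayed monitoring.

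The reply does not remove the contradiction. The SAP states an explicit start date that cannot be right for one of the two groups, and a listed time-to-event safety analysis has no other stated origin.

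**Conclusion.** Wrong as written; severity minor. For the delayed group, half of the monitored cohort, the SAP's stated start of active monitoring is about 122 days before the first patch is due. It conflicts with SAP section 4 and with Protocol section 4. The immediate group has a smaller mismatch of the same kind, because enrolment precedes activation.

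The effect is limited to measures that use this window as origin or denominator. For these, the planned wear share would be about halved with no assumed lag, and time to discontinuation would be about 4 months too long in the delayed group if the same start were applied. These sizes assume 30.44-day months, full planned wear, a final patch that ends 4 months after activation, and the activation lags shown.

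**What to change.** In SAP section 7, Descriptive Statistics, start each group's active monitoring period at activation of the first patch, as Protocol section 4 does. Keep the end at completion of the final patch.

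In SAP section 7, Analysis of Safety Endpoints, state the same origin for time to discontinuation and present the immediate and delayed groups separately.

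An activation origin leaves out subjects who never activate a patch, since they have no start date. SAP section 4 treats subjects who have not begun the first patch after three notifications as withdrawn, and it foresees delayed-group withdrawals before month 4. Report both kinds as separate counts by group, so that failure to start monitoring stays visible.

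The cost is two or three sentences in the SAP and no new data. According to SAP section 2, the Study Enrollment Database already holds activation dates and the dates of and reasons for withdrawal, and the device data hold recording start times.
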